3.8.3. Selection of Data in the Event of Multiple Records in a Window

Depending on the statistical analysis method, a single value may be required for each analysis window. For example, change from baseline by visit usually requires a single value, whereas a time-to-event analysis would not require one value per analysis window.

If multiple valid non-missing measurements exist in an analysis window, records will be chosen based on the following rules if a single value is needed, unless otherwise specified.

For baseline:

- The record closest to the nominal day for baseline will be selected except for HCV RNA, for which the latest record in the analysis window will be selected.
- If there are 2 records that are equidistant from the nominal day, the later record will be selected.
- If there are multiple records with the same time or no time recorded on the same day, the baseline value will be the average of the measurements for continuous data, or the measurement with the lowest severity (e.g., normal will be selected over abnormal) for categorical data.

For postbaseline values:

- The record closest to the nominal day for that visit will be selected except for HCV RNA, for which the latest record in the analysis window will be selected.
- If there are 2 records that are equidistant from the nominal day, the later record will be selected.
- If there is more than 1 record on the selected day, the average will be taken for continuous data and the worse severity (e.g., abnormal will be selected over normal) will be taken for categorical data, unless otherwise specified.

4. PARTICIPANT DISPOSITION

4.1. Participant Enrollment and Disposition

A summary of participant enrollment will be provided for each country, each investigator within a country, and overall by baseline Child-Turcotte-Pugh (CTP) class (CTP A, B, C, Unknown and total as defined in Section 6.1.3.2.3) and treatment group. The summary will present the number and percentage of participants in the All Enrolled Analysis Set. For each column, the denominator for the percentage calculation will be the total number of participants analyzed for that column.

A summary of participant disposition will be provided by treatment group and baseline CTP class and overall. This summary will present the number of participants enrolled and included in the FAS, the Safety Analysis Set, and the number and percentage of participants who completed the study and who did not complete the study (with summary of reasons for discontinuing registry). The denominator for the percentages of participants in each category will be the number of participants in FAS corresponding to that column. In addition, a flowchart will be provided to depict the overall disposition. A table of participant disposition for premature discontinuation of study by visit and reasons will also be displayed by treatment group and baseline CTP class.

A by-participant disposition listing with reasons for premature discontinuation of study and baseline CTP class will be provided by participant ID number in ascending order to support the above summary tables.

A separate listing of participants who prematurely discontinued registry will also be provided.

4.2. Extent of Exposure

This is a registry study with no active treatment. Extent of exposure to study drug is not applicable.

4.3. Protocol Deviations

Participants who did not meet the eligibility criteria for study entry but enrolled in the study, will be listed regardless of whether they were exempted by the sponsor or not. A by-participant listing will be provided for those participants who did not meet at least 1 eligibility (inclusion or exclusion) criterion. The listing will present the eligibility criterion (or criteria if more than 1 deviation) that participants did not meet and related comments, if collected.

Protocol deviations occurring after participants entered the study are documented during routine monitoring. A by-participant listing of important protocol deviations will be provided.

4.4. Assessment of COVID-19 Impact

This study was ongoing during the novel coronavirus (COVID-19) pandemic which had an impact on the study conduct. Some participants were unable to attend onsite visits due to shelter in place guidelines, site closures, or other reasons. This section describes how special situations due to COVID-19 will be handled in the analysis.

Information regarding missed or virtual visits due to COVID-19 will be collected as free text in the CRF comment fields. The determination of missed or virtual visits due to COVID-19 will be done using Natural Language Processing (NLP) to search the CRF comment, as described in Appendix 12.3. The summary tables and listing of participants with virtual visits or missing visits due to COVID-19 will be provided. Participants with any protocol deviations due to COVID-19 and registry premature discontinued participants due to COVID-19 will also be listed.

5. BASELINE CHARACTERISTICS

5.1. Demographics

Participant demographics variables (i.e., age, sex, race, ethnicity [Hispanic or non-Hispanic], and region [US or non-US]) will be summarized by treatment group, baseline CTP class (CTP A, B, C, Unknown and total) and overall for safety analysis set. Age will be summarized using descriptive statistics (n, mean, SD, median, Q1, Q3, minimum, and maximum). Age categories (< 65 years vs. ≥ 65 years), sex, race, ethnicity, and region will be summarized by the numbers and percentages of participants in each category. Age in years on Day 1 will be used or calculated from the registry start date.

The following items will also be added to the demographic summary table:

- Gap between the end of prior HCV treatment and the start of the registry as categories (<6 months vs. ≥6 months) (Registry start date - last day of parent study +1)
- Gap between SVR24 visit in parent study and the start of the registry as categories (<6 months vs. ≥6 months) (for non-commercial participants only)
- Duration of follow-up since the start of the most recent treatment in weeks
- Duration of follow-up since end of prior HCV treatment in weeks
- Duration of follow-up since the start of the registry in weeks (Last day of registry – registry start date +1)

A by-participant listing of demographics including the informed consent date, treatment regimen, treatment group, and baseline CTP class will be provided by participant ID number in ascending order.

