1.2. Registry Design

Design Configuration and Participant Population

GS-US-337-1431 is an observational study open to any cirrhotic participant with or without decompensated liver disease who have achieved SVR after receiving a SOF-based regimen

without IFN while participating in a Gilead-sponsored HCV study; or, at a subset of sites preselected by Gilead, who have previously received an all-oral SOF-based regimen outside a clinical study.

For participants enrolling from a Gilead parent protocol, the definitions of cirrhosis and of SVR are defined in the parent Gilead-sponsored treatment protocol. Participants who are enrolled after receiving an all-oral SOF-based regimen outside a clinical study, will have had cirrhosis confirmed prior to initiation of HCV treatment.

Once enrolled in the registry, participants will be followed for up to 5 years. For participants rolling over from a Gilead parent protocol, a Day 1 visit will be scheduled within approximately 60 weeks from a participant's projected SVR 24 visit in the parent protocol, or participants may enroll from the GS-US-248-0122 SVR registry study at any time with Sponsor approval. For participants who are enrolled after receiving an all-oral SOF-based regimen outside a clinical study, a Day 1 visit will be scheduled within approximately 2 years from the participant's SVR 12 date. Clinical visits will then occur every 24 weeks at Weeks 24, 48, 72, 96, 120, 144, 168, 192, 216, and 240.

Treatment Groups

This is a long-term observational follow-up registry study. No investigational medicinal product will be administered. The HCV regimen received in the parent studies will be used to assign treatment groups for analysis purposes. All the parent studies included in this registry are listed in Appendix 12.1.

Entry Eligibility Criteria

Participants must meet **all** of the following inclusion criteria to be eligible for participation in this study:

- 1) Willing and able to provide written informed consent;
- 2) Have previously participated in a Gilead-sponsored HCV study and received a SOF-containing regimen without IFN; OR

At pre-selected sites only, have received an all-oral SOF-based regimen outside a clinical study. These participants must have documentation of the regimen, start and end of treatment dates (month and year), and of having achieved SVR12;

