- 3) Have achieved SVR in a Gilead-sponsored study, as defined in the original treatment protocol; OR for participants who enroll after receiving an all-oral SOF-based regimen outside a clinical study, SVR will be defined as HCV RNA < LLOQ approximately 12 weeks following last dose of treatment;
- 4) Have liver cirrhosis, as defined in the original treatment protocol, and have not had a liver transplant after receiving a SOF-containing regimen; OR

Participants who enroll after receiving an all-oral SOF-based regimen outside a clinical study, will have had cirrhosis as diagnosed prior to initiation of HCV treatment.

Participants who meet **either** of the following exclusion criteria are not to be enrolled in this study:

- 1) Participant plans to initiate a new course of HCV therapy, including approved products and any investigational agents, during the course of this Registry;
- 2) History of clinically significant illness or any other major medical disorder that may interfere with participant follow-up, assessments, or compliance with the protocol.

Schedule of Assessments

Consent and demographics will be obtained at the Day 1 visit. The schedule of the full assessments is provided in the protocol and in Appendix 12.2.

Randomization

This is an observational study. Randomization will not be applied.

Registry Duration

Participants included in the study will be followed for up to 240 weeks (approximately 5 years), until early termination or completion of the study.

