12.2. Study Procedures Table

Clinical Assessments	Day 1 ^a	Study Week										
		24	48	72	96	120	144	168	192	216	240	ET
Informed Consent ^b	X											
Quality of Life Surveys	X	X	X	X	X	X	X	X	X	X	X	X
Adverse Events Related to Procedures	X	X	X	X	X	X	X	X	X	X	X	X
Limited Physical Exam ^c	X	X	X	X	X	X	X	X	X	X	X	X
Liver Disease Assessment ^d	X	X	X	X	X	X	X	X	X	X	X	X
Endoscopy	X									X		
Transient Elastography ^e	X		X		X		X		X		X	X
Liver Biopsy ^f											X	
Laboratory Assessments												
HCV RNA	X	X	X	X	X	X	X	X	X	X	X	X
Viral Sequencing ^g	X	X	X	X	X	X	X	X	X	X	X	X
Chemistry ^h	X	X	X	X	X	X	X	X	X	X	X	X
Hematology (Platelets)	X	X	X	X	X	X	X	X	X	X	X	X
Coagulation Test (PT/INR)	X	X	X	X	X	X	X	X	X	X	X	X
Additional Tests ⁱ	X	X	X	X	X	X	X	X	X	X	X	X
HCV RNA Confirmation ^j							X					

- a Day 1 visit to be conducted approximately 48 weeks from the final visit in the treatment protocol
- b Informed consent may be obtained prior to Day 1
- c Assessment of ascites, encephalopathy, height (at Day 1) and weight; calculated scores include BMI, CTP and MELD
- d Liver Disease Assessment: refer to protocol Section 6.3.5
- e At sites with a Fibroscan[®] or comparable equipment
- f **CCI**
- g Plasma will be collected for possible viral sequencing or other virology studies if indicated.
- h Includes ALT/SGPT, AST/SGOT, Albumin, Total bilirubin, Direct Bilirubin, Creatinine
- i Includes α -fetoprotein level, FibroTest[®], ELF panel, lipid panel, hemoglobin A1C, HOMA-IR and LOXL2
- j Only in participants with HCV RNA >LLOQ
- k For participants who consent

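### The SAP 5.1 row for the gap from end of HCV treatment to registry start is computed from the last day of the parent study: too short for rollover participants, undefined for commercial participants

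*SAP*

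**What the plan says.** SAP 5.1 (Demographics) adds five timing rows to the demographic table. The first is labelled "Gap between the end of prior HCV treatment and the start of the registry as categories", cut at 6 months, with the formula "Registry start date - last day of parent study +1". The second is "Gap between SVR24 visit in parent study and the start of the registry as categories", also cut at 6 months and restricted to non-commercial participants. The first row has no such restriction. A later row reports follow-up since end of prior HCV treatment in weeks, with no formula.

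Two places in the SAP time Day 1 for participants coming from a parent protocol. Section 1.2 schedules it "within approximately 60 weeks from a participant's projected SVR 24 visit in the parent protocol". Footnote a of the procedures table in Appendix 12.2 reads "Day 1 visit to be conducted approximately 48 weeks from the final visit in the treatment protocol". Section 1.2 also admits participants from the GS-US-248-0122 registry at any time with sponsor approval. For participants treated outside a study it requires documented treatment end (month and year) and schedules Day 1 within about 2 years of the SVR12 date.

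**The concern.** The label and the formula start from different dates. Rollover participants had to reach SVR in the parent study, and SVR is established some weeks after the last dose. The last parent-study day therefore falls after the end of treatment, and the error has one direction: the computed gap is shorter than the labelled gap.

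The neighbouring rows make a harmless reading difficult. If the parent study ended at the SVR24 visit, the first row repeats the second and the labelled quantity is not tabulated in categories at all. Since only the second row is limited to non-commercial participants, the first appears meant to include commercial participants, yet its formula needs a date they do not have. For entrants from GS-US-248-0122, the SAP does not say whether the last day is that of the treatment study or of the earlier registry.

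The registry clock for SVR durability and de novo HCC starts at Day 1. This row tells the reader how much post-treatment time had passed before observation began, by regimen and CTP class. A shortened gap makes entry look closer to treatment than it was.

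**Working it through.** The plan gives no numeric value for this gap, so there is no figure to reproduce. The check is date arithmetic.

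**Formulas.** Let T be end of treatment, L the last parent-study day and D the registry start date (Day 1).

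- Gap as labelled: D − T + 1
- Gap by the SAP formula: D − L + 1
- Shortfall: (D − T + 1) − (D − L + 1) = L − T

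**Inputs and assumptions.**

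- Entry window: 60 weeks = 420 days from the projected SVR24 visit (SAP 1.2).
- SVR24 visit at T + 168 days. This is assumed by analogy with the SVR12 wording, "SVR will be defined as HCV RNA < LLOQ approximately 12 weeks following last dose of treatment".
- Six months = 6 × 30.4375 = 182.6 days, so a gap of 182 days or less counts as under 6 months. The SAP does not define the month; this is an assumption.
- L − T is not stated for any of the 34 parent studies in SAP Appendix 12.1. Assumed values are 12, 24 and 36 weeks (84, 168 and 252 days, or 2.8, 5.5 and 8.3 months).
- For illustration, Day 1 is uniform over d = 0 to 420 days after SVR24, which is 421 possible dates. No document supports this distribution.

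**Gap as labelled.** It equals 169 + d, and is 182 or less for d = 0 to 13. Share under 6 months: 14/421 = 3.3%.

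**Gap by the formula.**

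- 24-week lag: the gap is d + 1, under 6 months for d = 0 to 181. Share 182/421 = 43.2%. Dates from d = 14 to 181 are placed in the wrong category: 168/421 = 39.9%.
- 12-week lag: the gap is d + 85, under 6 months for d = 0 to 97. Share 98/421 = 23.3%. Wrong category for d = 14 to 97: 84/421 = 20.0%.
- 36-week lag, using only Day 1 dates after the parent study ended (d = 84 to 420, 337 dates): the gap is d − 83, under 6 months for d = 84 to 265. Share 182/337 = 54.0%. The labelled gap is at least 169 + 84 = 253 days, so its share is 0%.

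**Alternative timing, Appendix 12.2 footnote a.** If D is 48 weeks = 336 days after L, the formula gives 337 days. The labelled gap is 337 + 84 = 421 days with a 12-week lag, or 337 + 168 = 505 days with a 24-week lag. Both are over 6 months, so the category is right. For the formula to return under 6 months, Day 1 must come within 181 days of the last parent-study day, which is 336 − 181 = 155 days (about 22 weeks) earlier than the footnote's timing.

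**Commercial participants.** L does not exist, so the formula returns nothing. For scale, take SVR12 at T + 84 days and Day 1 uniform over 0 to 728 days after it. The labelled gap is then 85 + d, under 6 months for d = 0 to 97, a share of 98/729 = 13.4%.

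**The case against.** The strongest reply is that the size is not in the documents. A reader might infer that the row understates time off treatment by 24 weeks in general, and that about 40% of participants will appear in the wrong category. Neither inference is supported. Section 1.2 refers only to a projected SVR24 visit and does not say when any parent study ended. Uniform entry is an illustration, and the one statement tying Day 1 to the final parent visit (about 48 weeks) implies almost no misclassification. That footnote and the 60-week wording need reconciling, but until then the range runs from near 0% to about 40% for lags of 12 to 24 weeks. This part of the reply stands.

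A reader might also infer that hardly anyone can enter within 6 months of treatment. Under the assumptions above that fits rollover participants (3.3%), but not commercial participants (about 13%).

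It can further be said that the same table reports follow-up since end of treatment and since registry start, so the difference in means recovers the mean gap. That is partly true. It recovers a mean and not the category shares, and it requires the follow-up row, which has no formula, to use the true end-of-treatment date.

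Finally, no endpoint depends on this row. Person-time in SAP 6.1.3.1 and 6.1.3.2.1 starts at the registry start date, and no hypothesis is tested. That stands and limits the weight of the point. It does not repair the conflict between label and formula or the missing commercial case.

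**Conclusion.** The row is wrong as written. Two conclusions follow from the text without distributional assumptions: the formula is too short by L − T for rollover participants, and it is undefined for commercial participants. For entrants from GS-US-248-0122 it is also ambiguous.

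The size is conditional. The shortfall is about 12 weeks if the parent study ended at an SVR12 visit, about 24 weeks if at SVR24, and more with longer follow-up. Under uniform entry over the 60-week window, 20% to 40% of rollover participants would change category for lags of 12 to 24 weeks; with Day 1 near 48 weeks after the final parent visit, close to none would.

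The consequence is confined to one two-category descriptive row. A reading that the durability, liver-event or HCC estimates are distorted is not supported. The point deserves correction because the row misstates what it names and the correction is cheap.

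**What to change.** Replace the formula with: registry start date − end date of the most recent HCV treatment + 1, for all participants, including those entering from GS-US-248-0122. State that the same end date is used in the row for follow-up since end of prior HCV treatment. Leave the SVR24 row as it is.

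For commercial participants with only month and year of treatment end, extend the day-01 partial-date rule of SAP 3.7 explicitly to this row, since it is now written for follow-up duration and time to events. Day 01 can lengthen the gap by up to 30 days, so a footnote should say that dates were imputed.

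Relabelling the row as the gap from the last parent-study day and limiting it to non-commercial participants would remove the contradiction, but would leave the time since treatment without a category row.

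The cost is one line of the SAP and one derivation. The treatment end date is already needed in SAP 6.1.3.1, 6.4.2 and 6.4.3, so no new data are required. Because the SAP is signed, the change belongs in its revision table or, under SAP section 1, in the CSR.

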5.2. Baseline Characteristics

Baseline characteristics include:

- Baseline liver function tests: CTP score/MELD score/AST to Platelet Ratio Index (APRI)/FibroTest score (Fibrosis score)/Elasticity (Fibroscan score)/Enhanced Liver Fibrosis (ELF) score/Fibrosis-4 (FIB-4) index as continuous variables
- Pretreatment HCV genotype and IL28B genotype (CC, CT, TT/missing categories)
- Baseline body mass index (BMI; in kg/m²) as a continuous variable and as categories (<30 kg/m², ≥30 kg/m²)

Baseline values are defined in Section 3.8.1 and 3.8.3. Data for baseline HCV genotype and IL28B (before entry into the parent study) are not collected in the registry study, and data collected at baseline of the parent study will be used for the analysis.

The above baseline characteristics will be summarized by treatment group, baseline CTP class (CTP A, B, C, Unknown and total) and overall for safety analysis set. Continuous variables will be summarized using descriptive statistics (n, mean, SD, median, Q1, Q3, minimum, and maximum) and categorical variables using the numbers and percentages of participants.

A by-participant listing of baseline characteristics including baseline CTP class will be provided by participant ID number in ascending order. Separate baseline characteristics by-participant listings will also be provided for participants who experienced virologic failure and who developed De Novo HCC during the registry study.

5.3. Medical History

Medical history data of clinical liver-associated events will be collected at screening and listed only. Medical history data will not be coded.

6. ENDPOINT ANALYSES

This analysis will be performed after all participants have completed approximately 240 weeks of follow-up or discontinued early from the study.

Primary and secondary endpoints will be summarized on the FAS (Section 3.1.2).

All statistical summaries and analyses will be performed using SAS[®] software (SAS Institute, Cary, North Carolina, USA).

6.1. Primary Endpoints

6.1.1. Definition of the Primary Endpoints

The primary endpoints are:

- The proportion of participants maintaining SVR at Week 240;
- The proportion of participants who develop liver disease progression or regression, as assessed by clinical and laboratory parameters;
- The proportion of participants who develop HCC through Week 240.

6.1.2. Statistical Hypothesis for Primary Endpoints

No formal statistical hypothesis is established for this study.

6.1.3. Primary Analysis of the Primary Endpoints

6.1.3.1. Proportion of Participants Maintaining SVR Through Week 240

Definition of Virologic Failure: Virologic failure is defined as having 2 consecutive blood samples (at least one week apart) with HCV RNA > LLOQ, or last available HCV RNA > LLOQ with no subsequent follow-up values. Date of virologic failure is the date of the first measurement if confirmed by 2 consecutive measurements, or the date of the last available HCV RNA > LLOQ with no subsequent follow-up values.

Participants who early terminated the study by a visit for a reason other than virologic failure are censored for that visit. In addition, participants who completed the study without a virologic failure are censored at the end of study by standard Kaplan-Meier (KM) methods.

Person-time pertaining to KM analysis of time to virologic failure will be calculated as: date of virologic failure (for participants who experienced virologic failure) or last day of registry (for participants who did not experience virologic failure) – registry start date + 1.

SVR end date will be the date to have HCV RNA level that was measurable during the registry study.

The KM estimate of the proportions of participants who maintained SVR, and the cumulative number of participants who experienced virologic failure, were at risk, and had been censored will be summarized by treatment group and by time point (Week 0, 24, 48, ..., 216 and 240), where Week 0 to 216 are the exact weeks elapsed since registry start date (i.e. 0, 168, 336, ..., and 1512 days), and Week 240 includes 1680 days elapsed since registry start date plus additional 30 days (i.e. 1710 days). The KM plots will also be presented in a figure.

A by-participant, by-visit listing of the actual HCV RNA value and \log_{10} HCV RNA will be provided by participant ID number in ascending order. A separate by-participant, by-visit listing of the actual HCV RNA value and \log_{10} HCV RNA will be provided for participants with virologic failure by participant ID number in ascending order, including time since registry start date to virologic failure, and time since the end of the most recent HCV treatment to virologic failure, parent study ID, most recent HCV treatment, and baseline CTP category.

Participants who experienced virologic failure more than 30 days after 240 weeks elapsed since registry start date (i.e. > 1710 days) will be listed separately.

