1.1. Registry Objectives

Primary Objectives

The primary objectives of this study are as follows:

- To assess the durability of SVR;
- To assess clinical progression or regression of liver disease, including the incidence of hepatocellular carcinoma (HCC) following SVR.

Secondary Objective

The secondary objective of this study is as follows:

- For participants who received their SOF-based regimen in a Gilead parent protocol, to determine whether subsequent detection of HCV RNA in participants who relapse following SVR represents the re-emergence of pre-existing virus, the development of resistance mutations, or re-infection.

Exploratory Objective

The exploratory objective of this study is as follows:

- **CCI** [REDACTED]

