6.2. Secondary Endpoints

The secondary endpoints are:

- The proportion of participants with detectable HCV RNA due to re-emergence of pre-existing virus through Week 240;
- The proportion of participants with detectable HCV resistance mutations through Week 240;

- The proportion of participants with detectable HCV RNA due to re-infection through Week 240.

Virologic relapse is defined as HCV RNA > LLOQ on two samples collected at least one week apart with the same virus present prior to treatment in the parent treatment protocol. Re-infection is defined as HCV RNA > LLOQ on two samples collected at least one week apart with a different virus than that present prior to treatment in the treatment protocol. HCV sequencing will be performed if HCV RNA is sufficient. These results will be listed in CSR by Clinical Virology.

No table will be provided for the secondary endpoints.

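### The primary SVR-durability Kaplan-Meier is an all-cause estimate that includes re-infection, but it is not labelled as such, and the SAP drops the relapse and re-infection summaries that the protocol planned

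*SAP*

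**What the plan says.** The first primary objective in SAP 1.1 is "To assess the durability of SVR". SAP 6.1.3.1 estimates it by Kaplan-Meier, by treatment group, with an event that can arise in two ways. The first is confirmed: "Virologic failure is defined as having 2 consecutive blood samples (at least one week apart) with HCV RNA > LLOQ". The second needs no confirmation: "or last available HCV RNA > LLOQ with no subsequent follow-up values". The censoring rule is: "Participants who early terminated the study by a visit for a reason other than virologic failure are censored for that visit".

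SAP 6.2 then divides confirmed viraemia by cause. For relapse: "Virologic relapse is defined as HCV RNA > LLOQ on two samples collected at least one week apart with the same virus" as before treatment. For re-infection: "Re-infection is defined as HCV RNA > LLOQ on two samples collected at least one week apart with a different virus". The results go to a listing: "These results will be listed in CSR by Clinical Virology". The same section says that the secondary endpoints get no table.

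Protocol 8.6.2 planned more: a summary of re-emergence of pre-existing virus by time point, with the model of the primary analysis, and a count and percentage by time point for re-infection. SAP 6.5 states that the endpoint analyses do not depart from the protocol.

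**The concern.** Loss of SVR can mean two things. The original infection can return, which concerns the lasting effect of the treatment. Or a cured participant can acquire a new virus, which concerns exposure after cure. The documents treat these as different, since telling them apart is the secondary objective. The primary estimate combines them under the name virologic failure, and the SAP provides no summary that separates them.

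At stake is how the main durability figure is read. Unless the report says that the curve covers any return of HCV RNA, readers may take the failure percentage as the rate of late relapse. No other estimate in the SAP corrects that reading.

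**Working it through.** **1. Is re-infection inside the primary event?**

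| Item | RNA condition | Virus condition |
|---|---|---|
| Virologic failure, route 1 (SAP 6.1.3.1) | two consecutive samples above LLOQ, at least one week apart | none |
| Virologic failure, route 2 (SAP 6.1.3.1) | last value above LLOQ, nothing after it | none |
| Relapse (SAP 6.2) | two samples above LLOQ, at least one week apart | same virus |
| Re-infection (SAP 6.2) | two samples above LLOQ, at least one week apart | different virus |

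Re-infection is the route 1 criterion plus a virus condition, so every re-infection confirmed on consecutive samples is a primary event. Censoring does not remove it, because only exits for reasons other than virologic failure are censored. Protocol 3.2 uses one RNA trigger for relapse and re-infection together, and Protocol 8.6.1 does not mention re-infection. No section censors it or treats it as a competing event.

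**2. Does any other summary separate the causes?** SAP 6.2 gives a listing only. The virologic-failure listing in SAP 6.1.3.1 names HCV RNA values, times to failure, parent study, most recent treatment and CTP category, but no relapse or re-infection class. The Protocol 8.6.2 summaries have no counterpart in the SAP.

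**3. Which failures can be classified?** Sequencing needs sufficient HCV RNA (Protocol 6.3.2, SAP 6.2). For participants treated outside a study it is optional (Protocol 6.3.2), and the secondary endpoints exclude them (Protocol 8.1.3). A route 2 failure meets neither two-sample definition in SAP 6.2.

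**4. Size.** The documents give no failure count, relapse rate, re-infection rate or planned sample size, so there is no stated figure to reproduce. All rates and shares below are assumptions.

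*By share of failures.* With all-cause failure F = 1.0% and re-infection share s, relapse failure is F × (1 − s):

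| s | Relapse failure | Maintained SVR, all-cause | Maintained SVR, relapse only | Gap (points) | F ÷ relapse failure |
|---|---|---|---|---|---|
| 0 | 1.00% | 99.0% | 99.00% | 0 | 1 |
| 0.25 | 0.75% | 99.0% | 99.25% | 0.25 | 1.33 |
| 0.50 | 0.50% | 99.0% | 99.50% | 0.50 | 2 |
| 0.75 | 0.25% | 99.0% | 99.75% | 0.75 | 4 |

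*By rate.* SAP 6.1.3.1 sets the Week 240 horizon at 1710 days, so T = 1710 / 365.25 = 4.68 years. With constant hazards λ (relapse) and ρ (re-infection), all-cause SVR = exp(−(λ + ρ)T) and relapse-only SVR = exp(−λT). With λ = 0.1 per 100 person-years, relapse-only SVR is 99.53%:

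| ρ per 100 person-years | All-cause SVR | Gap (points) | Re-infection share of failures |
|---|---|---|---|
| 0 | 99.53% | 0 | 0% |
| 0.1 | 99.07% | 0.46 | 50% |
| 0.3 | 98.14% | 1.39 | 75% |
| 1.0 | 94.98% | 4.55 | 91% |
| 2.0 | 90.64% | 8.90 | 95% |

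Varying λ from 0.05 to 0.3 hardly changes the gap (8.81 to 8.92 points at ρ = 2.0), so the gap depends on the re-infection rate.

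*Competing event or censoring.* At λ = ρ = 0.1, relapse risk is 1 − exp(−λT) = 0.467% with re-infection censored, and λ/(λ + ρ) × (1 − exp(−(λ + ρ)T)) = 0.466% as cumulative incidence. At low rates the choice makes almost no difference.

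**The case against.** The strongest reply is that nothing is wrong with the estimate. Where the documents define SVR themselves, for participants treated outside a study (Protocol 4.1, SAP 1.2), it is HCV RNA below LLOQ about 12 weeks after the last dose, whatever the virus. A participant with confirmed viraemia no longer maintains that state. Cause is assigned on purpose to the secondary objective, and no section limits durability to relapse. All-cause counting is also conservative, since it cannot put maintained SVR above a relapse-only figure. If failures are few, a reader could separate the sequenced cases by hand from the listings. All of this stands, and it is why the Kaplan-Meier should be kept.

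It does not answer the reporting gap. The secondary analysis that was to carry the split has been reduced to a listing, against Protocol 8.6.2 and without acknowledgement in SAP 6.5. A hand count from a listing is not adjusted for censoring.

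A reader might go further and infer that the SAP blames each regimen for re-infections, or that re-infection will distort comparisons between regimens. The documents do not support either. Treatment group is a descriptive grouping, no hypothesis is tested, and there are no data on exposure risk by regimen.

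**Conclusion.** The point holds as one of labelling and a missing summary. The primary event includes re-infection by definition, the curve is not described as all-cause, and the SAP as written yields no estimate that separates late relapse from new infection. The departure from Protocol 8.6.2 is unrecorded.

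A reader might infer that the primary estimate is invalid or that durability will be materially understated. The first does not follow, because all-cause maintenance of SVR is a legitimate quantity. The second cannot be judged from the documents. At 1.0% all-cause failure and re-infection shares of 25% to 75%, the gap is 0.25 to 0.75 points. Gaps of several points require assumed re-infection rates of about 1 per 100 person-years or more, for which the documents give no source. With no re-infection there is no gap. The ratios of 1.33 to 4 show only how far the failure percentage could mislead if read as a relapse rate. The change is worth making because it is cheap and restores what the protocol planned.

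**What to change.** - Keep the Kaplan-Meier of SAP 6.1.3.1 and label it in text, table and figure as all-cause loss of SVR, including re-infection.
- Beside it, for participants from Gilead parent protocols, report the Week 240 estimate of same-virus relapse with sequence-confirmed re-infection as a competing event. Censoring re-infection is acceptable at low event rates if the SAP says so.
- Report the number and percentage with re-infection in the same participants, as Protocol 8.6.2 planned.
- Show failures that are unsequenced, or that rest on one unconfirmed last value, as undetermined. Bound the relapse estimate by counting them once as relapse and once as not relapse.
- Keep participants treated outside a study under the all-cause definition only.
- Correct SAP 6.5 so that it records any Protocol 8.6.2 summary that is still omitted or changed.

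The cost is SAP wording and one small table or curve with its bounds. Sequencing is already planned where HCV RNA suffices, so no new data are needed. Some failures may stay unclassified, and the bounds will show how much that matters.
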